## 6.3. Data Collection Dates

The implementation of the BH-VPN will begin in June among patients with a completed telepsychiatric consult.

## 7. PROJECT TIMELINE

Project Timeline	2017								2018			
	May	June	July	Aug	Sept	Oct	Nov	Dec	Jan	Feb	Mar	Apr
Initial IRB Submission												
Site/Teammate Training (SIV)												
Prepare Methods manuscript												
Registration with Clinical Trials.gov												
First Patient on Study												
Last Patient on Study												
Study Duration												
Final Data Analysis												
Internal white paper												
Manuscript Prep and Submission												
Conference Presentation/Posters												

## 8. INTERVENTION PLAN

### 8.1. Navigator Assessments

The initial assessment within 72 hours will capture the following components:

- Communication method
- Insurance
- Primary care provider
- Outpatient Psychiatry provider
- Collateral resource
- Recent visit summary
- Substance abuse
- Medication barriers
- Appointment Barriers
- Transportation needs
- Access to medications
- Community Resources
- Columbia-Suicide Rating Scale to assess for suicide ideation

### 8.2. Follow-up Assessments

The weekly follow-up contact assessments are comprised of the following components:

- Columbia-Suicide Rating Scale to assess for suicide ideation
- Appointment reminder/follow-up
- Medication access barriers
- Substance use disorder follow-up
- Supportive listening
- Psychoeducation
- Utilization of community resources
- Crisis planning and adherence to the plan by the patient

### 9.1. Protocol and Pathway Training

Background, protocol and process steps will be presented to psychiatrists and nurse practitioners who will be providing virtual psychiatric consultations. The role of virtual patient navigator and randomization scheme will be presented so expectations are clear that this is not available every day/time or weekends. This will be presented at the Department of Psychiatry meeting, which includes Emergency and Telepsychiatry Departments. Attendees may also include providers, who at some point may see patients who have been through this pathway, but will not be directly involved in providing evaluations. Education will be provided to the emergency department staff involved in this project, so that they are aware of the process and the role of the virtual patient navigator.

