## **4.3. Inclusion\Exclusion Criteria**

### **4.3.1. Inclusion Criteria**

Eligible patients must meet each of the following criteria:

- Present to an ED at participating sites
- Completed a telepsychiatric consult as captured in the electronic medical record
- Telepsychiatric consult completed Monday through Friday during the Navigator's potential hours of operation
- $\geq 18$  years of age at time of ED admission

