## **5.2. Randomization and Allocation**

Randomization for the purposes of this project, will be based on days the Navigators are available to treat patients who've completed their telepsychiatric consult per the BH-VPN or usual care. Patients may be in the ED for multiple days. Their enrollment status depends on the day and time of their initial telepsychiatric consultation. Navigation will only be available for those patients whose consult occurs during intervention day/times. As part of the research design and rollout of this project, randomization will occur at the day level with the days being identified as intervention or usual care days for the duration of the study. We expect an average of 3.7 patients seen daily for both hospitals combined. Patients will accrue in both arms of the study Monday through Friday during the hours of operation. Patients will not be accrued on days where the navigators are not available such as weekends, nights, and holidays.

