## 6.2. Statistical analysis

All analyses will follow intention to treat such that patients will be analyzed based on the allocated intervention on the day of their ED visit (BH-VPN or treatment as usual). We will compare the two groups on age, sex, suicide ideation, and neurocognitive disorders to assess for balance, which is inferred with randomization.

The primary outcome, inpatient admission  $\leq 5$  days, will be compared between the two groups of patients using a chi-square test. We will explore differences by site by conducting stratified analysis by hospital. We will attempt to adjust for the correlation among patients seen on the same day using a generalized linear mixed model with a log link and random effect for day, nested within hospital. If convergence problems arise due to small sample sizes, we will collapse by week rather than day. We will also control for hospital as a fixed effect in the model. Results for group comparisons will be presented with odds ratios and 95% confidence intervals.

Secondary outcomes are 45-day post discharge utilization (yes/no), 90-day post discharge utilization (yes/no), QCC defined 30-day readmission (yes/no), and patient centric 30-day readmission (yes/no). Each of the secondary outcomes are dichotomous and will be compared using the same approach as the primary outcome. All tests will be two sided and the data will be analyzed using SAS Enterprise Guide version 6.1. For all outcomes, we assume if there are no visits in the CHS electronic medical record that the value for having a visit is null; therefore, there will be no missing data for the primary or secondary outcome measures.

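### Sections 5.2 and 6.2 define the arm by different days, and under the 5.2 rule nothing described conceals upcoming days from staff who can partly influence consult timing

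*Combined protocol and SAP*

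**What the plan says.** Randomisation is by day, "with the days being identified as intervention or usual care days for the duration of the study" (section 5.2). On the individual patient, 5.2 says: "Their enrollment status depends on the day and time of their initial telepsychiatric consultation". The same section notes: "Patients may be in the ED for multiple days". Eligibility also depends on timing. One inclusion criterion in 4.3.1 begins "Telepsychiatric consult completed Monday through Friday during the" and goes on to require the navigator's potential hours of operation.

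Section 6.2 uses a different anchor for the intention-to-treat analysis: "patients will be analyzed based on the allocated intervention on the day of their ED visit".

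On disclosure, section 9.1 says that the background, protocol and process steps "will be presented to psychiatrists and nurse practitioners who will be providing virtual psychiatric consultations", and continues: "The role of virtual patient navigator and randomization scheme will be presented so expectations are clear". The rest of that sentence gives the purpose, which is to explain that navigation is not offered at all times. For the ED, 9.1 says: "Education will be provided to the emergency department staff involved in this project". The topics named for ED staff are the process and the navigator's role, not the scheme.

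No section says who holds the list of days, when each day's status is released, or that later days are concealed.

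**The concern.** There are two linked problems.

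The first is a contradiction. With two rules for the arm, the primary comparison is not defined for every eligible patient. Following 6.2 literally puts some patients in the arm that they were not managed in, and leaves others with no arm.

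The second is a risk that exists under the 5.2 rule. If staff know or can guess which days have a navigator, the consult of a patient thought suitable for supported discharge could be timed to fall on such a day. Section 2 records a reason to want this: psychiatrists report admitting patients because nobody is available to arrange outpatient follow-up. Such patients would probably convert less often than average. Moving them would lower conversion on intervention days and raise it on usual-care days even if navigation did nothing. Intention to treat cannot repair this, because the selection comes before the arm is set. The one planned balance check (6.2) covers age, sex, suicide ideation and neurocognitive disorders. It does not look at consult delay.

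**Working it through.** **1. The two rules side by side**

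- Arrival and consult on the same weekday: 5.2 and 6.2 agree.
- Arrival on a usual-care Tuesday, first consult on an intervention Wednesday: 5.2 gives intervention, and navigation can be offered. If the day of the ED visit means the arrival day, 6.2 gives usual care.
- Arrival on Sunday, first consult on Monday in navigator hours: eligible under 4.3.1, and 5.2 gives Monday's arm. Under 6.2 there is no arm, because weekend days are not randomised.

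The documents do not say how many stays cross midnight or a weekend, so the number affected cannot be computed.

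**2. The plan's own sample size**

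Inputs from 6.1: 50% against 35%, alpha 0.05, power 85%; two-sided from 6.2. The two-proportion formula gives 194 per arm without continuity correction and 207 with it. Then 2 × 207 = 414 and 414 × 1.1 = 455.4, rounded up to 456. Both stated figures reproduce, and 456 / 2 = 228 per arm.

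**3. Size of the bias if consults are moved selectively (5.2 rule)**

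From the plan: 228 per arm, 50% conversion, design effect 1.1. Assumed, and not in the documents: no true effect; a fraction f of usual-care-day patients moved to an intervention day; conversion r among those moved.

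- Usual care after the move: (0.50 − f·r) / (1 − f)
- Intervention after the move: (0.50 + f·r) / (1 + f)
- Difference: 2f(0.50 − r) / (1 − f²)

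Example with f = 10%, r = 20%: 0.48 / 0.90 = 53.3%; 0.52 / 1.10 = 47.3%; difference 0.2 × 0.30 / 0.99 = 6.1 points. The last column is the chance that a two-sided 5% test, with variance multiplied by 1.1, rejects.

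| f | r | Usual care | Intervention | False reduction | Rejection rate |
|---|---|---|---|---|---|
| 5% | 50% | 50.0% | 50.0% | 0 points | 5% |
| 5% | 20% | 51.6% | 48.6% | 3.0 | 9% |
| 5% | 10% | 52.1% | 48.1% | 4.0 | 13% |
| 10% | 50% | 50.0% | 50.0% | 0 | 5% |
| 10% | 20% | 53.3% | 47.3% | 6.1 | 23% |
| 10% | 10% | 54.4% | 46.4% | 8.1 | 37% |

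The bias is zero if moved patients have average risk, and it changes sign if they convert more often than 50%.

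**4. Would counts alone reveal it?**

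Moving 5% changes 228 and 228 to about 217 and 239, a gap of 0.10 × 228 = 22.8. Moving 10% gives about 205 and 251, a gap of 45.6. If counts vary as Poisson (an assumption), the standard error of the gap is √456 = 21.4. The gaps are then about 1.1 and 2.1 standard errors. Counts are a weak signal at 5%, so consult delay should be examined as well.

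**The case against.** The strongest reply has four parts.

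- A reader might infer from 9.1 that the calendar of days is handed to clinicians. The text does not say so. Read to its end, the sentence only sets the expectation that navigation is intermittent, and the scheme may mean no more than the day-level principle. This stands. What remains is that the plan does not restrict the list, and staff will in any case see whether a navigator is on that day.
- A reader might infer that the consult clinicians control the timing. Sections 4.1 and 5.3 say that an ED physician identifies the patient and makes the referral. Influence is therefore partial and shared, and the ED staff who start the process are not named as being shown the scheme. This also stands.
- Section 5.2 ties status to the initial consult, so a repeat consult cannot change the arm. The telepsychiatrist's recommendation follows the consult, so selective timing needs an earlier impression of prognosis. Both narrow the route without closing it, since an ED physician could form that impression.
- Under 6.2 read literally, moving a consult does not change the analysed arm, so the table above would not apply. That is correct. The result would instead be navigated patients counted as usual care, with eligibility still tied to consult time. Section 6.2 cannot be credited as a safeguard while it contradicts 5.2 and leaves weekend arrivals unassigned.

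The wording in 6.2 may be loose shorthand for the consult day. If so, the correction is trivial, but it still has to be written down.

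**Conclusion.** The contradiction between 5.2 and 6.2 is established from the text and needs no assumption beyond the multi-day stays that 5.2 itself mentions. The two sections must be reconciled before analysis.

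The concealment point holds as a risk. Arm and eligibility depend on a consult time that staff can partly influence, a reason to prefer navigator days is on record, and no concealment of later days is described. It would be tempting to conclude that consults will be moved, or that the trial carries a bias of about 6 points. The documents support neither. The share moved and the conversion of those moved are both assumed. For 5-10% moved, the false reduction runs from 0 points (moved patients convert at 50%) through about 3 to 6 (at 20%) to about 8 (10% moved, 10% conversion), against a design difference of 15 points. These figures apply only if arm follows the consult day. The sample size is not in question.

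**What to change.** - **Section 6.2, primary analysis.** Use one arm definition, the day of the initial consult as in 5.2.
- **Section 6.2, sensitivity analysis.** Repeat the primary comparison with each patient assigned to the allocation of the first eligible day at or after ED arrival. Consult timing cannot change that assignment, and weekend arrivals get an arm. It does not address patients whose consult falls outside navigator hours and who are therefore not in the study.
- **Section 9.1.** Present only the day-level concept. Keep the day list with the statistician, and with the navigators for staffing. Release each day's status to clinical staff only at the start of navigator hours.
- **Reporting.** Give consults per day and time from ED arrival to consult, both by arm. Same-day release alone does not prevent a patient being held on a usual-care day in the hope of a navigator later, so these checks are needed as well.

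The cost is small: shorter scheduling notice for clinical staff, a few lines in 6.2 and 9.1, and a little more analysis. No extra patients are needed. The checks assume that arrival and consult times can be drawn from the electronic record.

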## 10. SAFETY RISKS AND REPORTING

The data collection and intervention for this project presents no more than minimal risk to patients. However, patients who present to the ED with a behavioral health crisis are considered a high-risk population. The implementation of the BH-VPN and its components complement ongoing patient care through virtual patient navigation within CHS. The addition of an evaluation design that aligns with existing patient care where there are limited resources thus confers minimal additional risk to patients. Resource constraints do not allow for the virtual patient navigation to be offered on all days allowing for a natural experimental design.

Implementation of new innovative techniques in the usual care process potentially introduces an increased possibility for care elements that are less effective, as effective, or more effective in providing quality of care. To address additional risk, or increased time without direct visual and in-person medical supervision we will collect the following potential adverse events: deaths, and reported events of suicidal ideation. These events will be weighed against average expected rates in this population by independent providers and experts in behavioral health and research, who will serve on a data and safety monitoring board.

Other potential risks of participation in this project include, the risk of health information disclosure. There is always the risk of disclosure of a patient's private health information (PHI) or medical information. However, the processes identified in this protocol to enable the execution of this project, do not increase inherent risk of disclosure. Carolinas HealthCare System utilizes several hard and soft safety controls in the protection of patient information and medical records. Security controls include, but are not limited to, multiple system firewalls, access restrictions to patient records and information, locked offices and buildings housing research and patient data, and multiple layers of username and password protected computer and system access. The project team will ensure that appropriate handling of patient PHI follows standard CHS procedure. In the event of PHI disclosure, the appropriate internal departments will be informed and processed per legislation and privacy regulations.

### 10.1. Data and Safety Monitoring Board (DSMB)

Per the NIH, A DSMB is an independent advisory body of experts appointed to assess, at regular intervals, the progress of a trial, review accumulating data, evaluate safety event reports, and determine critical efficacy endpoints in a manner that contributes to the safety of subjects and the continued validity and scientific merit of the trial. Due to the project's high risk population, this protocol will be monitored according to the protocol-specific data and safety monitoring plan, and will abide by standard operating procedures set forth by both the Carolinas Healthcare System Office of Clinical and Translational Research and CORE. It is the responsibility of the Principal Investigator to monitor the safety data for this study. The Principal Investigator, Statistician, and other team members will meet as needed to review enrollment and retention, safety data for all subjects, study progress, and validity/integrity of the data. Documentation of these meetings will be kept with study records. The Principal Investigator will submit data to the project-specific Data and Safety Monitoring Board according to the overarching Data and Safety Monitoring Plan.

## **10.2. Data Quality Assurance**

This study will be organized, performed, and reported in compliance with the study protocol, standard operating procedures (SOPs) of the CORE and CHS OCTR, and other applicable regulations and guidelines (e.g. GCP).

## **10.3. Safety Reporting to the IRB**

All events occurring during the conduct of a protocol and meeting the definition of a reportable safety event per the Chesapeake IRB guidelines, will be reported to the IRB within 10 working days of the Investigator learning of the event, per their requirements.

Major protocol deviations that result in a threat to subject safety or the integrity of the study will be reported to the IRB per their requirements.

## **10.4. Safety Monitoring by the Sponsor**

The conduct of this project will abide by standard operating procedures set forth by both CHS OCTR and CORE. It is the responsibility of the Principal Investigator to monitor the safety data for this study. The Principal Investigator, Statistician, and other team members will meet as needed to review enrollment and retention, safety data for all subjects, study progress, and validity/integrity of the data. Documentation of these meetings will be kept with study records.

# **11. RESEARCH COMPLETION**

The Principal Investigator has the right to close the project at any site any time.

For any of the above closures, the following applies:

- Closures should occur only after consultation between involved parties.
- All affected institutions must be informed as applicable, according to local law.
- In case of a partial study or site closure, patients still participating in the COPD clinical pathway, or those who are considered in follow-up, must be taken care of in an ethical manner.

The study will be considered complete when one or more of the following conditions is met:

- The enrollment period has ended, and the data collection period is complete.
- All subjects have dropped out or discontinued from the study after the enrollment period is completed, but prior to data collection cutoff as described in section 8.3.
- The IRB, DSMB, or Principal Investigator discontinues the study.
- The Principal Investigator defines an administrative or clinical cut-off date.
- The DSMB deems the study inefficacious or unsafe.

Upon study completion, a final report will be presented to the Executive Committee and all key stakeholders. The final report will detail all findings including primary, secondary and exploratory outcomes. The team will also prepare a manuscript for publication focused on outcomes and feasibility of implementation of the transition clinic.

## **12. ETHICAL AND LEGAL ISSUES**

### **12.1. Ethical and Legal Conduct of the Study**

The procedures set out in this protocol, pertaining to the conduct, evaluation, and documentation of this study, are designed to ensure that the Investigators abide by Good Clinical Practice (GCP) guidelines and under the guiding principles detailed in the Declaration of Helsinki. The study will also be carried out in keeping with the applicable local laws and regulation(s).

Documented approval from appropriate agencies (e.g. IRB) will be obtained before the start of the study, per GCP, local laws, regulations, and organizations.

Strict adherence to all specifications laid down in this protocol is required for all aspects of study conduct; the Investigators may not modify or alter the procedures described in this protocol.

Modifications to the study protocol will not be implemented without consulting the Principal Investigator and the IRB, as applicable. The Principal Investigator must assure that all study personnel, including co-investigators and other study staff members, adhere to the study protocol and all applicable regulations and guidelines regarding research both during and after study completion.

The Principal Investigator will be responsible for assuring that all the required data will be collected and properly documented.

### **12.2. Confidentiality**

All records identifying the subject will be kept confidential and, to the extent permitted by the applicable laws and/or regulations, will not be made publicly available.

### **12.3. Disclosure of Data**

The Principal Investigator, his associates and co-workers, and the appropriate regulatory agencies may use the information and data included in this protocol as necessary for the conduct of the study. Information contained in this study, and data and results from the study are confidential and may not be disclosed without the written permission of the Principal Investigator.

### **13. RETENTION OF RECORDS**

Essential documentation including all IRB correspondence, will be retained for at least 2 years after the investigation is completed. Documentation will be readily available upon request.

### **14. PUBLICATION POLICY**

The Principal Investigator or designee must send any draft manuscript, abstract, or conference presentation to members of the project Executive Committee for feedback and transparency, prior to submission of the final version. The Principal Investigator will be responsible for all relevant aspects regarding data reporting and publication.

The Principal Investigator or designee will ensure that the information and results regarding the study will be made publicly available on the internet at [www.clinicaltrials.gov](http://www.clinicaltrials.gov).

[figure not shown]

## APPENDICES

### APPENDIX 1: Patient Navigation

This diagram shows the contact points among patients receiving care by the BH-VPN.

### APPENDIX 2: Suicide Ideation steps

This diagram shows the procedure if a patient is identified with suicidal ideation from the CSSRS screening tool. This tool is administered during each phone contact.
